8.1.1 PATIENT CHARACTERISTICS

The following characteristics will be reported for all treatment cohorts at baseline.

- Demographic Characteristics: Age, BMI, Smoking

Age (years) at index date will be calculated as Age = year (index date)-year (birth).

Four age groups are defined (in years): 45-49, 50-59, 60-69 and 70 and over.

BMI (Body Mass Index) will be calculated for each patient as the weight in kg divided by square of height in meters. BMI will be calculated using the following formulas:

$$BMI (kg/m^2) = Weight (kg) / (Height (m))^2$$

Or

$$BMI (kg/m^2) = 10000 \times Weight (kg) / (Height (cm))^2$$

- BMI will be categorized into four groups as follows:
- Underweight: BMI <18.5 kg/m²
 - Normal range: 18.5 ≤ BMI <25 kg/m²
 - Overweight: 25 ≤ BMI <30 kg/m²
 - Obese : BMI ≥30 kg/m²
- Smoking will be defined as three categories; Current Smokers, Former Smokers and Never Smokers. A 'Current Smoker' will be defined as a patient who is currently smoking at the index prescription date, a 'Former Smoker' as a patient that has a past history of smoking but has stopped prior to the index prescription date. A 'Never Smoker' will be defined as a patient that has no history of smoking (The reported frequency of smoking may be very low because smoking status is under recorded in Italian and Spain databases)
 - Alcohol use. Alcohol use will be defined as three categories; Current Drinkers, Former Drinkers and Never Drinkers. A 'Current Drinker' will be defined as a patient who is currently drinking alcohol as at the index prescription date, a 'Former Smoker' as a patient that has a past history of drinking alcohol but has stopped drinking prior to the index prescription date. A 'Never Drinker' will be defined as a patient that has no history of drinking alcohol. (The reported frequency of alcohol use may be very low because alcohol use is under recorded in Italian and Spain databases).
 - Use of relevant concomitant medications, e.g., hormone replacement therapy. (A concomitant medication is any medication used during BZA/bisphosphonate/raloxifene treatment defined as the total treatment duration between the first and the last prescription of BZA/bisphosphonate/raloxifene.)
 - Medical History VTE (Venous Thromboembolic Events), Diabetes, Hypertension, and Malignancies (including Breast, Renal, Thyroid, Ovarian, Gastrointestinal tract, Lung) and aggregate of all malignancies.

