8.1.4 TIME TO EVENT ANALYSIS

A time to event analysis to compare the risk between treatment cohorts, i.e., the BZA, raloxifene and bisphosphonate treated groups, will be conducted for the primary end point (VTE) and other secondary endpoints if sufficient data are available,

[figure not shown]
The time to an event will be calculated as the time from index prescription date to the incidence date of primary end points. If a patient does not have a primary end point, the treatment duration will be based upon the index prescription date to the last visit or end of follow-up period, whichever comes first.

In order to ensure the exact duration from the start of treatment to the incidence of primary endpoints, a subgroup of newly prescribed patients who were diagnosed with osteoporosis during the enrolment period will be used first.

In the very unlikely event that the number of bisphosphonate or raloxifene patients are less than the number of BZA patients, the analysis will be extended to include bisphosphonate and raloxifene patients whose treatment began prior to the enrolment period. Considering the fact that bisphosphonates and raloxifene were launched before BZA (See the figure below), some patients could have already gotten treatment of bisphosphonates and raloxifene prior to the enrolment period (i.e., before BZA was launched). For such patients the start date will be the first date of treatment for bisphosphonates or raloxifene, available within the database.

Figure 1. Calculation of duration (from start date to the incidence of primary endpoint) for the treatment cohorts

The time to event analysis model will also be used to test for differences in time to event while adjusting for covariates of interest.

This model will take into account the duration to the incidence of the endpoint and control for imbalances in outcome risk factors, as determined based on the baseline descriptive analysis.

The following factors possibly related to the incidence of the primary end point will be considered.

- Treatment group (BZA, raloxifene, and bisphosphonate)
- Age
- BMI
- Reported history of smoking (If the reported frequency of smoking status is low this will be excluded)
- Reported Medical History of Diabetes, Hypertension, Malignancies
- Time since diagnosis of osteoporosis
- Previous treatment for osteoporosis (before index date) or Number of different treatments for osteoporosis in the entire patient history available
- History of DVT or PE

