- Previous history of major lower extremity (hip, knee) arthroplasty, arthroscopic surgery (information on arthroscopic surgery not available in Italian database)
- General surgery, major orthopedic surgery (<1month prior to incidence of VTE)
- (Information on general surgery not available in Italian database)
- Multiple trauma (<1month prior to incidence of VTE)
- Hip, pelvis, or leg fracture (<1month prior to incidence of VTE)
- Stroke (<1month prior to incidence of VTE)
- Acute spinal cord injury (paralysis) (<1month prior to incidence of VTE)
- Hormone replacement therapy (limited information available in both databases)

A Cox model will be used in order to take into account the time varying component. The time from the beginning of the treatment (one among three types, BZA, raloxifene, and bisphosphonate) to the occurrence of primary end point is fitted in this model. The Proportional Hazards (PH) assumption will be tested for each covariable. If the PH assumption does not hold for some covariates, the use of time-varying HR for those covariates will be explored. If a categorical variable with more than 2 levels does not satisfy this PH assumption, collapsing some categories will be attempted to satisfy the PH assumption. Correlations between variables will also be evaluated in order to find independent factors and a final model that is clinically relevant.

First, the univariate analysis will be carried out on each covariable in order to determine the explanatory variables to be included in the final multivariate model. All significant variables with a p -value ≤ 0.20 in the univariate model will be taken into account in the multivariate Cox model.

If > 80% of the important risk factors for VTE listed above does not satisfy the PH assumption, a logistic regression analysis would be performed instead of Cox model to otherwise determine if the covariable is related to the incidence primary endpoint (VTE). The dependent variable would be the incidence of the primary end point during the follow-up period categorized as a binary variable. The 2 indicators of treatment group (BZA vs. bisphosphonates, raloxifene, will be forced in the multivariate model (Cox model or logistic model) to analyze incidence in each class of treatment, adjusted on

significant factors. Hazard ratios (HR) (odds ratios (OR) in case of logistic regression) with 95% Confidence intervals (CIs) and p-values will be presented.

[figure not shown]
Patients Switching Medications

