8.2 STATISTICAL ANALYSES

8.2.1 PATIENT CHARACTERISTICS

Descriptive statistics on available patient characteristics (e.g. age, BMI, smoking, history of relevant medical diagnoses) will be reported for all exposure groups at index date. A summary table will present and compare all the patients' demographic data at index date (BZA/raloxifene/bisphosphonates).

- Age (years): derived by difference between the year of time of interest and year of birth.
- Weight (kg): recorded at the given date, or if not available, at the most recent date before or it
- Height (cm): the value at the given date or, if not available, at the most recent date before or after it.

- Body Mass Index (BMI) (kg/m^2), calculated from weight and height as defined previously. BMI will be described in quantitative measure and in categorical data, as usual
- Alcohol use
- Smoking status
- Time since diagnosis of osteoporosis: derived by the difference between the index date and the diagnosis date.
- Previous treatment for osteoporosis (before index date) (yes versus no) or Number of different treatments for osteoporosis in the entire patient history available
- Previous history of VTE (Venous Thromboembolic Events) (before index date)
- Previous history of major lower extremity (hip, knee) arthroplasty, arthroscopic surgery (information on arthroscopic surgery not available in Italian database)
- General surgery, major orthopedic surgery (<1month prior to incidence of VTE) (information on general surgery not available in Italian database)
- Multiple trauma, (<1month prior to incidence of VTE)
- Hip, pelvis, or leg fracture (<1month prior to incidence of VTE)
- Stroke (<1month prior to incidence of VTE)
- Acute spinal cord injury (paralysis) (<1month prior to incidence of VTE)
- Hormone replacement therapy (limited information available in both databases)

If the diagnoses for any of the conditions listed in this section (8.2.1) are not found in the database, they will be assumed to be absent.

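### SAP 8.1.1 labels on-treatment HRT as baseline, and Cox covariates in 8.1.4 have post-index, event-anchored or unstated windows that can distort the adjusted drug hazard ratio

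*SAP*

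**What the plan says.** **Baseline label.** SAP 8.1.1 opens with "The following characteristics will be reported for all treatment cohorts at baseline", and Protocol 7.2 also places concomitant medication at baseline. Within that list SAP 8.1.1 says: "A concomitant medication is any medication used during BZA/bisphosphonate/raloxifene treatment defined as the total treatment duration between the first and the last prescription". HRT is the example given. In the same section, smoking, alcohol and medical history are tied to the index date or earlier.

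**Model covariates.** The candidate list in SAP 8.1.4 carries the entry "Hormone replacement therapy (limited information available in both databases" with no time window. It also offers "Previous treatment for osteoporosis (before index date) or Number of different treatments for osteoporosis in the entire patient history available". The first option stops at index; the second names no end date. SAP 8.2.1 repeats the pair under a heading sentence that says patient characteristics "will be reported for all exposure groups at index date". Surgery, multiple trauma, leg or pelvic fracture, stroke and spinal cord injury are each listed as occurring within one month before VTE.

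**Timing elsewhere.** SAP 8.1.4 says that adjustment is for imbalances seen in the baseline description. SAP 8.2.4 takes the model factors as they stand at the event or at the visit before it. The part of 8.1.4 on switching takes switchers' covariates at the event or at the end of follow-up. Only the exposure cohort is declared time-dependent, and only in the as-treated approach. SAP 7 treats an unrecorded condition or treatment as absent.

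**The concern.** A covariate that is fixed in the model but classified from later data can be positive only in women who stayed event-free, and for HRT stayed on treatment, long enough to acquire it. Their waiting time is credited to the positive group although no event could have occurred in it. A woman with an early VTE who had not yet started HRT is coded as a non-user, not as missing. The covariate therefore looks protective even if it does nothing. If the arms differ in how often women become positive, part of that artefact moves into the drug HR. The treatment count is the more exposed of the two, because the SAP itself says in 8.1.4 that exposure changes are often due to treatment failure or side effects.

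The covariates for the month before VTE raise a different problem. A woman without VTE has no such month. If she is simply coded as negative, the factor can be present only in cases, and its HR is inflated by construction.

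At stake are the adjusted Cox HRs, which SAP 4.2 and 8.2.2 name for the comparison of the drugs. The baseline table would also no longer describe the women at cohort entry.

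**Working it through.** The plan gives no figure on this point, so there is none to reproduce. The size was found by simulation.

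**Inputs from the documents:** VTE rate 1.74 per 1,000 person-years and 15% annual loss (Protocol 7.1); follow-up of at most 5 years (Protocol 6.1.1); 1,823 bazedoxifene (BZA) and 10,938 bisphosphonate women (SAP 5.4).

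**Assumptions not in the documents:** the yearly rates of starting HRT or a second osteoporosis drug; mean treatment duration of 2 years for HRT; nobody positive at index.

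**Method.**
1. Draw event time T as exponential with rate 0.00174, the same in both arms (true drug HR 1).
2. Draw censoring C as the smaller of 5 years and an exponential with rate −ln(0.85) = 0.1625. Observed time is t = min(T, C).
3. Draw covariate start S and drug stop D. For HRT, a woman is flagged if S < min(D, t). For the second drug, she is flagged if S < t. The covariate has no effect on T (true HR 1).
4. Fit a Cox model at 100 times the study size, first with drug only, then with drug and flag. Repeat with a flag of equal prevalence fixed at index.

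| Start rate per year, BZA / bisphosphonate | Flagged, BZA / bisphosphonate | Covariate HR | Drug HR unadjusted | Drug HR adjusted | Ratio | With index-date flag: drug HR, covariate HR |
|---|---|---|---|---|---|---|
| HRT 0.03 / 0.03 | 4.1% / 4.2% | 0.653 | 0.987 | 0.987 | 1.000 | 0.987, 1.003 |
| HRT 0.10 / 0.03 | 12.7% / 4.2% | 0.665 | 0.967 | 1.001 | 1.035 | 0.972, 0.940 |
| Second drug 0.30 / 0.10 | 58.1% / 27.7% | 0.399 | 1.037 | 1.425 | 1.374 | 1.045, 0.975 |

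The unadjusted values differ from 1 by chance; the ratio within a row is the result. Smaller runs of the 0.10 / 0.03 case gave ratios of 1.021/0.979 = 1.043 and, with a true drug HR of 2, 2.285/2.178 = 1.049. They rest on 1,913 and 2,262 events, against 7,616 in the table, so the table value is preferred.

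**Hand check.** With flagged shares of person-time q1 (BZA) and q0 (bisphosphonate) and covariate HR h, the ratio is about [1 − q0(1 − h)] / [1 − q1(1 − h)]. The shares come from simulated cohorts with the same inputs.
- HRT 0.10 / 0.03: q1 = 0.150, q0 = 0.049, h = 0.665 gives 0.984/0.950 = 1.036.
- Second drug: q1 = 0.703, q0 = 0.346, h = 0.399 gives 0.792/0.577 = 1.37.

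**Scale against the study's precision.** Mean follow-up is (1 − 0.85^5)/0.1625 = 3.42 years. Expected events under HR 1 are 1,823 × 3.42 × 0.00174 = 10.9 and 10,938 × 3.42 × 0.00174 = 65.1. The standard error of the log HR is √(1/10.9 + 1/65.1) = 0.33. The HRT shift is ln 1.035 = 0.03, about a tenth of that. The second-drug shift is ln 1.374 = 0.32, about one standard error.

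**The case against.** Several points on the other side are sound.

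- **The HRT window in the model is inferred.** SAP 8.1.4 does not refer back to 8.1.1. The 8.1.1 window is the natural reading because no other is given for HRT, but the text does not state it. The alternative timing in 8.2.4 is no remedy, since it too lies after index.
- **The count may be meant as a look-back.** It is an either/or option, and SAP 8.2.1 lists it among index-date characteristics. A reader might infer that the plan counts later switches. The wording permits this but does not say it, and the +37% applies only on that reading.
- **HRT may matter little.** It is kept only at a univariate p-value of 0.20 or less, and the SAP says that information on it is limited. A covariate HR near 0.65 also assumes that nobody uses HRT at index. With 5% on HRT at index and 1% per year starting, a true HR of 1 is estimated at 0.86 to 0.92. A spurious association can, however, help a covariate pass the screen.
- **Height.** A reader might add height to the list, because SAP 8.2.1 allows "the value at the given date or, if not available, at the most recent date before or after it". Adult height is nearly constant, so a later value creates no immortal time. In simulation the drug HR stayed at 0.97 to 0.98, even when complete-case inclusion depended on a height recorded after index.
- **The primary result.** A reader might infer that the main incidence comparison is biased. SAP 8.1.2 makes unadjusted cumulative incidence primary, and 8.2.4 calls time-to-event analysis secondary. Neither the crude rates nor the univariate drug HRs use these covariates.

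The contradiction between the baseline label and the on-treatment window remains, as does the missing reference date for the event-anchored covariates.

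**Conclusion.** The point holds for HRT and other concomitant medication, for the unbounded treatment count, and for the covariates tied to the event date. As written, the SAP mislabels part of the baseline table and leaves room for adjusted Cox HRs that condition on the future.

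The distortion of the drug HR is about 0 to 3.5% for HRT, small beside the study's imprecision. It is up to about +37% for the count, if post-index switches are included and the arms switch at 0.30 and 0.10 per year. All start rates and durations behind these figures are assumptions. With equal rates in the arms the HRT shift is nil. The effect of the event-anchored covariates was not quantified, because the SAP does not define their value in women without VTE.

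**What to change.** 1. In SAP 8.1.1, define HRT and other concomitant medication from prescriptions in the 6 months up to and including the index date. Report on-treatment use separately, and not as baseline.
2. In SAP 8.1.4 and 8.2.1, keep only osteoporosis treatment before the index date, or end the count at index.
3. If on-treatment HRT, or surgery, trauma, fracture, stroke and cord injury within the previous month, are wanted in the model, enter them as time-dependent covariates. Evaluate them at each event time for every woman still at risk, with or without VTE.
4. Reconcile the covariate timing in SAP 8.1.1, 8.1.4 (including the text on switching), 8.2.1 and 8.2.4. The rule on height can stay.

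The cost is SAP wording and a little programming. Inclusion already requires 6 months of data before index, so no new data are needed. A 6-month look-back may miss some earlier HRT use.

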7 HANDLING OF MISSING VALUES

For each variable, the number and proportion of patients missing data for each treatment group will be specified. The primary analyses will be done using only the information available in the unmodified dataset. Smoking status, alcohol consumption, height and/or weight (BMI) values are known to be missing for approximately 40-60% patients in the Cegedim LPD based on previous studies. (Age of patients will always be known as it is a selection criterion). Dates are automatically recorded in the Cegedim LPD and doctors can select diseases codes from the pre-defined lists. In all analyses, if a condition (disease or treatment) other than the diagnosis of osteoporosis is not recorded, it will be assumed to be non-existent.

To estimate the effect of missing data, two additional analyses for the primary study endpoint will be conducted. First, the analyses will be repeated utilizing a dataset in which cases with missing values of main study covariates of BMI, smoking status and alcohol status are excluded. The disadvantage to this approach is the reduction in the sample size. Another disadvantage to this approach is that the subjects with missing values may be different than the subjects without missing values (e.g., missing values that are not missing at random), resulting in a non-representative sample after removing the cases with missing values. Second, multiple imputations for the missing values of BMI, smoking status, alcohol status will be used in the second set of analyses and compared to complete case analyses to understand the potential impact of missing data on results [2].

Outlier

Extreme values for weight and height will be searched for. If a value seems implausible, as regard to gender or ratio weight/height, it will be put as missing.

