Venous Thromboembolic Events (VTE) are defined as deep vein thrombosis, pulmonary embolism, retinal vein thrombosis, and venous sinus thrombosis. This objective is to compare this incidence in real life settings with validated diagnosis codes, ICD9 in Italy and International Classification of Primary Care (ICPC) codes in Spain.

The availability of medical history of all relevant medical diagnosis for patients will be checked in both the Spanish and the Italian database and presented if available. The variables of medical history (diabetes, hypertension, VTE and Malignancies) will be presented in classes (Yes/No) before index date. (All the detailed diagnosis codes of each endpoint have been validated by Pfizer and are available in a separate reference document). For all medical history and smoking status, if the relevant information is not found in the database, it will be assumed to be negative.

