8.2.5 SUMMARY OF STATISTICAL ANALYSIS

Analyses for Primary Objective and Secondary Objective 1

Comparator: BZA vs. bisphosphonate (primary objective), BZA vs. raloxifene (secondary objective 1).

Study endpoint: VTE.

Populations: a. Full BZA full raloxifene, random age stratified bisphosphonate subgroup
b. Incident user subgroup.

Statistical Method:

- i. Incidence rate, cumulative method (*Total new cases during follow-up period / Total persons at risk during follow-up period*) with stratification by risks of interest e.g. Age, BMI.
- ii. Univariate and multivariate incidence rate by incidence density (*Total new cases during follow up period / Total person years during follow-up period*)*1000) method using Cox regression model and a Likelihood Ratio Test for testing Hazard Ratio (HR) =1 (ratio of hazard in BZA population vs. bisphosphonate/raloxifene population) with covariates associated with VTE outcome and exposure (Drug groups).

Sensitivity analyses:

- i. Repeat analysis will be conducted that compares using a 30-day and a 90-day definition of recent exposure with using the 60-day definition.
- ii. Missing Data: First, the analyses will be repeated utilizing a complete dataset in which cases with missing values of main study covariates of BMI, smoking status and alcohol status have been deleted. Second, multiple imputation for the missing values of BMI, smoking status, alcohol status will be used in the second set of analyses.

Multiple imputation procedure:

- 1) Estimate distribution of BMI, smoking status and alcohol status according to patients whose data are available.
- 2) For the patients who had missing values those variables draw values of the variables from the distribution from 1).
- 3) With the imputed dataset (including none-missing data), estimate HR as described.
- 4) Repeat 2)-3) for m times, and record HR of each time.
- 5) Calculate mean of m estimates of HR.
- 6) Adjust variance of HR with the following formula, and use the variance to calculate confidence interval.

$$V = \left(1 + \frac{1}{M}\right) V_B + V_W.$$

V_B is the between imputation variance, and V_W is within imputation variance.

Analyses for Secondary Objective 2 and Secondary Objective 3

Comparator: BZA vs. bisphosphonate (secondary objective 2), BZA vs. raloxifene (secondary objective 3).

Study endpoint: Secondary endpoints.

Population: a. Full BZA, full raloxifene, random age stratified bisphosphonate subgroup.
b. Incident user subgroup

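### SAP 8.1.1 codes unrecorded smoking as negative while SAP section 7 treats it as missing, and no passage says which coding feeds which analysis

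*SAP*

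**What the plan says.** SAP 8.1.1 (Patient Characteristics) ends with a default rule: "For all medical history and smoking status, if the relevant information is not found in the database, it will be assumed to be negative". The same section defines three smoking categories (current, former, never) and accepts that "smoking status is under recorded in Italian and Spain databases".

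SAP section 7 (Handling of Missing Values) takes another line. It states: "Smoking status, alcohol consumption, height and/or weight (BMI) values are known to be missing for approximately 40-60% patients in the Cegedim LPD". It asks for the number and proportion missing for each variable in each treatment group. It then plans two extra analyses of the primary endpoint. The first uses a "dataset in which cases with missing values of main study covariates of BMI, smoking status and alcohol status are excluded". The other is described so: "Second, multiple imputations for the missing values of BMI, smoking status, alcohol status will be used in the second set of analyses". SAP 8.2.5 repeats both analyses for the primary and the secondary endpoints. Its first imputation step is: "Estimate distribution of BMI, smoking status and alcohol status according to patients whose data are available".

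Smoking is a candidate covariate in the time-to-event model (SAP 8.1.4), which allows it to be left out if its reported frequency is low.

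**The concern.** A patient with no smoking entry is either a non-smoker (8.1.1) or a patient with a missing value (section 7). The two codings give different baseline tables, different adjusted hazard ratios, and different content for the missing-data analyses. Two programmers could follow the SAP faithfully and disagree, and the choice could be made after the data are seen.

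The 8.1.1 coding also has a predictable fault. The SAP itself says smoking is under-recorded, so an absent entry is weak evidence of not smoking. The group labelled non-smoker would contain smokers whose status was never entered, and adjustment for smoking would then be incomplete if smoking differs between drug groups.

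**Working it through.** **1. Does any other text settle it?** Setting the rules side by side:

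- The assume-absent rule in section 7 covers diseases and treatments. The one in 8.2.1 covers diagnoses. Neither names smoking; only 8.1.1 does.
- Section 7 says the primary analyses use the dataset unmodified and asks for missing counts per variable. A recode to negative fits neither.
- Alcohol, equally described as under-recorded in 8.1.1, has no assume-negative rule.
- No sentence limits the 8.1.1 rule to the baseline table, or says that the section 7 analyses return to the raw field.

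So the text does not resolve the conflict.

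**2. How many patients are affected?** Group sizes are from SAP 5.4: 1,823 bazedoxifene, and 1,823 × 6 = 10,938 bisphosphonate (reproduces the plan's figure). The unrecorded share m is 0.4 to 0.6, from section 7; this is one approximate range shared by three variables.

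- Bazedoxifene: 1,823 × 0.4 = 729; 1,823 × 0.6 = 1,094.
- Bisphosphonate: 10,938 × 0.4 = 4,375; 10,938 × 0.6 = 6,563.

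Under section 7 these patients are excluded or imputed for smoking. If the 8.1.1 recode is done first, the number left to exclude or impute for smoking is 0 in both groups. BMI and alcohol stay missing, so both analyses still run.

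**3. What could it do to the adjusted ratio?** The documents give neither smoking prevalence by drug group nor a smoking-VTE ratio. Both are assumptions here, as are no drug effect, equal follow-up per patient, and recording that is independent of true status.

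Let p be true smoking prevalence, R the smoking rate ratio, and N the group size. After the recode:

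- labelled smokers: N·p(1−m), relative rate R;
- labelled non-smokers: N·[1−p(1−m)], relative rate (p·m·R + 1−p) / (1−p(1−m)).

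The crude ratio is (p₁R + 1−p₁)/(p₀R + 1−p₀). The adjusted ratio is Mantel-Haenszel over the two labelled strata, with stratum weight w = N₁N₀/(N₁+N₀).

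Worked case: 20% vs 10% smokers, R = 2, m = 0.4.

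- Crude: 1.2/1.1 = 1.091.
- Labelled smokers: 218.8 and 656.3 patients, w = 164.1, rate 2 in both groups.
- Labelled non-smokers: 1,604.2 and 10,281.7 patients, w = 1,387.7, rates 0.96/0.88 = 1.0909 and 0.98/0.94 = 1.0426.
- Adjusted: (2×164.1 + 1.0909×1,387.7)/(2×164.1 + 1.0426×1,387.7) = 1.038.
- Share of log bias left: ln 1.038/ln 1.091 = 0.43.

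| Smokers, BZA vs bisphosphonate | R | Crude | Adjusted, true smoking | Adjusted, recoded (m = 0.4 to 0.6) | Log bias left |
|---|---|---|---|---|---|
| 15% vs 10% | 1.5 | 1.02 | 1.00 | 1.01 (1.010 to 1.015) | 43-63% |
| 20% vs 10% | 2 | 1.09 | 1.00 | 1.04 to 1.06 | 43-63% |
| 40% vs 20% | 2 | 1.17 | 1.00 | 1.07 to 1.11 | 46-66% |

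**4. Unequal recording.** With 20% smokers in both groups and R = 2, the crude ratio is 1.00. If 40% are unrecorded in one group and 60% in the other, adjusting on the recoded variable gives 0.97 or 1.03, depending on which group is recorded better. Here the recode creates the bias. With equal smoking and equal recording the result is 1.00.

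**The case against.** The strongest defence is that 8.1.1 is a baseline-description section and section 7 is the dedicated missing-data section. If assume-negative is only a default, and the section 7 analyses go back to the raw field, those analyses are exactly the check that the default needs. That is a sensible reading, but the SAP does not state it, so the ambiguity stands.

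The numerical effect is also small. The Protocol's own Table 3 interval at an incidence rate ratio of 1, for 1,750 vs 10,500 patients, is 0.6 to 1.8; a shift to 1.01 or even 1.11 is minor beside it. That stands, and it limits the weight of the point.

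A reader might infer four stronger things, which the documents do not support:

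- *That the missing-data analyses are emptied and could never reveal the problem.* This needs the recode to come first, which is not stated, and even then only smoking is lost.
- *That smoking is an established confounder here.* Section 7 calls it a main covariate, but 8.1.4 lists it only among factors possibly related to VTE. No imbalance between drug groups is reported.
- *That the recode triggers the removal of smoking from the model.* It lowers apparent frequency (20% true smoking would show as 12% at m = 0.4 and 8% at m = 0.6), but 8.1.4 sets no threshold for low. If smoking is dropped, or fails the 0.20 univariate screen, its coding does not touch the adjusted hazard ratio.
- *That the primary result is biased.* SAP 8.1.2 makes cumulative incidence the primary approach and 8.2.4 calls the time-to-event analysis secondary, although 4.2 does use Cox hazard ratios for the comparisons. The crude incidence figures do not use smoking.

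**Conclusion.** The contradiction is real and unresolved in the text. The 8.1.1 rule, applied literally, gives roughly two-fifths to three-fifths of each group a default non-smoker label, if the shared 40-60% range holds for smoking.

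The consequence for the adjusted hazard ratio is conditional and modest. In the scenarios with a smoking imbalance, about 43-66% of the log confounding bias remains. Unequal recording alone moves a null result by about 3% either way, and balanced smoking with balanced recording gives no bias. These sizes rest on assumed prevalences and smoking ratios, and on recording that is independent of true status. The plan should be corrected because the rule is wrong as written and easy to repair, not because a large bias has been shown.

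**What to change.** - In SAP 8.1.1, delete the words 'and smoking status' from the default sentence, so that assume-negative covers diagnoses only.
- Keep unrecorded smoking as missing, as section 7 does, and show a 'not recorded' row for each treatment group in the baseline table.
- In 8.1.4, judge whether reported smoking is too infrequent to keep in the model among patients with a recorded status.
- In section 7, state that the complete-case and imputation analyses use the raw smoking field, and state which smoking coding the main Cox model uses. Without that statement, a standard Cox fit that includes smoking would silently drop the unrecorded patients. The complete-case and imputation analyses can stay as additional analyses; this point does not require promoting either to the main model.

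The cost is one or two SAP sentences and an extra table row. No new data are needed.
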